Specific aims: **1)** Determine if dyads in the TIP-C+SMSH as compared to the SMSH alone group created by the first randomization will have: a) lower depression, anxiety, and summed severity of 13 other symptoms at weeks 1-12, 13, and 17 (primary outcomes); b) lower use of healthcare services (hospitalizations, urgent care or emergency department [ED] visits) during 17 weeks (secondary outcomes); c) greater self-efficacy, social support, and lower caregiver burden during weeks 13 and 17 (potential mediators). **2)** Among nonresponders to the SMSH alone after 4 weeks, determine if dyads assigned to TIP-C+SMSH as compared to the SMSH alone group created by the second randomization will have better primary and secondary outcomes and potential mediators at weeks 5-12, 13, and 17. **3)** Test the interdependence in survivor's and caregiver's primary and secondary outcomes. **4)** Determine which characteristics of the dyad are associated with responses to the SMSH alone during weeks 1-4 and optimal outcomes for the dyad during weeks 1-12, 13 and 17 so as to determine tailoring variables for the decision rules of individualized sequencing of interventions. Findings will be used to improve symptom management and reduce distress in survivor-caregiver dyads.

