Sample size and power considerations. To determine sample size, we started at the right of the schematic in Figure 1 (the second randomization) and moved from right to left to determine the needed number of consenting dyads. To power the comparisons on primary outcomes for the groups created by the second randomization (Aim 2), we used the effect size of Cohen’s $d=0.39$ (adjusted for baseline), the smallest seen in the preliminary data for TIP-C against an educational intervention (Table 1) to conservatively estimate sample size requirements. We further adjusted this effect size for the reduction in error variance due to 10 repeated measures of primary outcomes. In past studies, Pearson correlation coefficients between pairs of repeated measures of depression, anxiety and summed severity of other symptoms ranged from $r=0.36$ to 0.77, resulting in the range of the adjusted effect sizes from $d=0.54$ to 0.84. Using the smallest adjusted $d=0.54$, the required sample size is 60 per group created by the second randomization, for power of .80 or greater in two-tailed tests at the 0.05 level of significance.

Moving from left to right in Figure 1 (schematic), 120 dyads from two groups created by the second randomization will be non-responders to the SMSH alone. From past work, response rate to the SMSH on depression and anxiety was approximately 30%,²²⁸ therefore 120 non-responders will be 70% of 172 randomized to the SMSH alone in the first randomization. The comparison of these 172 to 60 dyads allocated to the TIP-C+SMSH in the first randomization will have power of 0.95 to detect the effect size of 0.54 (adjusted for the repeated measures) in testing the hypothesis associated with Aim 1. The tests of mediation and interdependence effects in Aim 3 will have an even greater power because of further reduction in error variance. Aim 4 is exploratory, thus formal power considerations are not applicable. In summary, the total

required post-attrition sample size for all specific aims is N=232. To account for 22% attrition based on past work, we will need 298 dyads to consent.

Recruitment and retention of participants.

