Randomization. Following the baseline interview, dyads will be randomized to either SMSH alone (N=172 post-attrition) or to TIP-C+SMSH (N=60 post-attrition). A minimization algorithm will be programmed by [name] to balance arms by recruitment location, site of cancer, stage of cancer (early versus late), type of treatment, and survivor's relationship to the caregiver (spouse vs non-spouse).²³⁹ The second randomization will occur for those who do not respond to the SMSH alone after the first 4 weeks using the same approach as the first randomization except in 1:1 ratio. The study coordinator will run the computer algorithm from the main study office (Tucson) to ensure allocation, concealment, and blinding.

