
Design. We selected the SMART design (Figure 1) for this study over alternative designs (e.g., implementation designs) because the SMART design allows a precision or personalized approach to determine the right treatment at the right dose with the right sequence for the right survivor-caregiver dyad. SMART designs, although newer, show promise in developing the sequences of evidence-based interventions for more efficient and individualized patient- and caregiver-centered care. We will use findings from this study to create an algorithm for clinically meaningful decision making about symptom management for survivors and their caregivers to be tested in future implementation/dissemination studies. We will recruit 298 cancer survivors undergoing chemotherapy, targeted therapy, or hormonal therapy for a solid tumor at the NCI designated University of Arizona Comprehensive Cancer Center (UACC, Tucson and Phoenix locations) and at Arizona community oncology settings. The survivors will be screened for moderate or severe depression and/or anxiety prior to enrollment and identify the informal caregivers who will participate in the study. Following enrollment, informed consent and baseline interview of both survivor and caregiver, the dyad will be randomly assigned to either: 1) SMSH alone or 2) TIP-C+SMSH for 8 weeks followed by continued SMSH alone for 4 weeks. During 12 weeks following initial randomization, all participants will receive weekly telephone contacts to assess symptoms, deliver the assigned intervention and assess its enactment and fidelity. After the initial 4 weeks in the SMSH alone group, the survivor’s response to the intervention will be determined. If the survivor responds (defined as a reduced score on depression and/or anxiety) (See C9a. Primary Outcomes), the dyad will continue with the SMSH alone for 8 more weeks. If the survivor is a non-responder (defined as no improvement or a worsening score for depression and/or anxiety), the dyad will be re-randomized to either continue with SMSH alone for 8 more weeks, or add 8 weeks of TIP-C. The rationale for using the survivor’s response as the criterion for re-randomization is from the extensive evidence of interdependence in survivor and caregiver outcomes presented, and on the caregiver’s focus on the survivor’s outcomes. The rationale for timing of the assessment of response and re-randomization to add the TIP-C intervention after 4 weeks is based on past testing of the SMSH,^{15,16,30} where median time to response on psychological distress ranged from 14 to 24 days. Post-intervention and follow-up telephone assessments are at weeks 13 and 17.

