Aim 1, Hypothesis 1: Dyads initially randomized to the TIP-C+SMSH will report lower depression, anxiety, and summed severity of other symptoms at weeks 1-12, 13, and 17, and lower unscheduled health services use, higher self-efficacy and social support, and lower caregiver burden at weeks 13 and 17 as compared to those initially randomized to the SMSH alone. This hypothesis will be tested using statistical model #1 that relates repeated measures of the survivor or caregiver outcome y (one at a time) to the group assignment variable xx_1 , outcome at baseline xx_2 , time entered as a class variable to model potentially non-linear patterns, and other covariates. For normally distributed outcomes, this model will be fit as a linear mixed effects model (LME). Generalized linear mixed effects (GLME) modeling will be used if outcome is not normally distributed and cannot be normalized using transformations. For health service use, statistical model #1 will be implemented as a GLME model with Poisson distributed errors, or as a zero-inflated Poisson or negative Binomial model based on the distribution of the counts of different health services uses. Each type of health services use (e.g., hospitalizations, ED visits) will be analyzed separately. The explanatory variables including study group will be evaluated as predictors of zero inflation (whether or not the count is zero), and also as predictors of the magnitude of the count when it is not zero. The main effects of the group variable xx_1 will be tested.

Aim 2, Hypothesis 2: Dyads where survivors do not respond to the SMSH alone during weeks 1-4 and have TIP-C added during weeks 5-12, will report lower depression, anxiety, and summed severity of other symptoms at weeks 5-12, 13, and 17, and lower unscheduled health services use, higher self-efficacy and social support, and lower caregiver burden at weeks 13 and 17 as compared to those who are re-randomized to continue with the SMSH alone. The strategy described under the analyses for Aim 1 will be implemented for the repeated outcome measures during weeks 5-12 and weeks 13 and 17 that will be related to group assignment from the second randomization, symptom severity during week 4, time, and covariates.

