Secondary outcomes. Secondary outcomes are caregivers' and survivors' hospitalizations, urgent care or ED visits during the study. In baseline, week 13 and 17 interviews over the telephone, each dyad member will be asked to recall ED visits and admissions to hospitals and, if they occurred, their reasons and duration. Recall period will be 3 months in baseline and week 13, and 1 month in week 17 interviews. Extensive previous research²⁻⁵ documents self-report is a reliable and valid method to collect health services use data especially when standardized methods are used and the recall period is short, as in this project. Self-report is the only reasonable and cost-effective way to assess healthcare use, as it would be impossible to access health (medical) records across the multiple systems and payers used by participants in this study.

Potential mediators.

Caregivers' and survivors' self-efficacy. PROMIS 4-item short forms (sf) will be administered in interviews.²⁵³⁻²⁵⁶ Self-efficacy specific to symptom management will be captured by the GSDS item described above.

Caregivers' and survivors' social support. PROMIS 4-item-sf for emotional support and PROMIS Informational Support 4a will be used in interviews.²⁵³⁻²⁵⁶

Caregiver Reaction Assessment Tool.²⁵⁷ This caregiver burden tool was developed and validated with caregivers of patients with chronic conditions. It has 5 subscales: impact on schedule, caregiver's esteem, family support, impact on health, and impact on finances, with Cronbach's alphas exceeding 0.70.

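### Aim 2 health service use takes in about 4 weeks of events from before the second randomisation, which pulls its rate ratio toward 1

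*Combined protocol and SAP*

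**What the plan says.** - **Timing of the second randomisation** (section 4.0, Randomization): "The second randomization will occur for those who do not respond to the SMSH alone after the first 4 weeks". Section 5.0 (Design) adds that for a non-responder "the dyad will be re-randomized to either continue with SMSH alone for 8 more weeks, or add 8 weeks of TIP-C".
- **Aim 2 window** (section 2.0): the group given TIP-C "will have better primary and secondary outcomes and potential mediators at weeks 5-12, 13, and 17". Secondary outcomes are included in that statement.
- **How service use is collected** (section 6.0, Secondary outcomes): only in the baseline, week-13 and week-17 interviews. "Recall period will be 3 months in baseline and week 13, and 1 month in week 17 interviews". For content, "each dyad member will be asked to recall ED visits and admissions to hospitals and, if they occurred, their reasons and duration". Event dates are not mentioned.
- **Aim 2 analysis** (section 5.0, Analytic Methods, repeated in section 8.0): the Aim 1 strategy "will be implemented for the repeated outcome measures during weeks 5-12 and weeks 13 and 17", related to "group assignment from the second randomization, symptom severity during week 4, time, and covariates". For service use, the Aim 1 strategy is a Poisson mixed model, or a zero-inflated Poisson or negative binomial model, with a test of the group main effect.
- **Power** (section 4.0): "To power the comparisons on primary outcomes for the groups created by the second randomization (Aim 2"). No event rate, rate ratio or power is given for service use.

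**The concern.** The two post-baseline recall periods add up to about 17 weeks, so together they run from roughly the first randomisation. That suits Aim 1. For Aim 2 it means the week-13 count mixes about 4 weeks before the second randomisation with about 9 weeks after it. TIP-C had not yet been added for anyone in the Aim 2 comparison during those first 4 weeks, so it cannot have changed those events.

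For symptoms, the Aim 2 model resets the starting point to week-4 severity. Service use gets no matching step. The reference to weeks 5-12 does not help, because service use is never collected weekly. Followed as written, the plan gives a rate ratio for weeks 1-17, not for the post-randomisation period that section 2.0 sets for Aim 2.

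**Working it through.** **Inputs.** From the documents: 3 months of recall at week 13 (taken as 13 weeks), 1 month at week 17 (taken as 4 weeks), second randomisation after week 4, and 60 dyads per Aim 2 group. Assumed, because the documents give none: event rates, the true rate ratio (RR), and full effect of TIP-C from week 5. There is no stated figure for service use to reproduce.

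**Share of the window before the second randomisation.** Week 13: 4/13 = 31%. Both counts: 4/17 = 24%.

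**Expected ratio at a uniform rate.** Week 13: (4 + 9·RR)/13. Both counts (a Poisson model with time as a class variable and a group main effect gives the ratio of totals): (4 + 13·RR)/17. Share of log effect lost: 1 − ln(observed)/ln(RR).

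| True RR | Week 13 | Loss | Both counts | Loss |
|---|---|---|---|---|
| 0.50 | 0.654 | 39% | 0.618 | 30% |
| 0.70 | 0.792 | 35% | 0.771 | 27% |
| 0.90 | 0.931 | 32% | 0.924 | 24% |

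For RR 0.70: (4 + 6.3)/13 = 0.792 and (4 + 9.1)/17 = 0.771.

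**Sensitivity at RR 0.70.**
- If weeks 1-4 hold a share s of control-group events, the ratio over both counts is s + (1 − s)·0.70. With s = 0.15 it is 0.745 (loss 17%); with s = 0.35 it is 0.805 (loss 39%).
- If the recall reaches back only 12 weeks, the ratios are (3 + 6.3)/12 = 0.775 at week 13 and (3 + 9.1)/16 = 0.756 over both counts.

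**Power.** z = |ln ratio| / √(1/E0 + 1/E1 + 2k/60), where E0 and E1 are expected events per group and k is overdispersion. At 0.02 events per week, RR 0.70 and 60 per group:
- Planned count: E0 = 60·0.02·17 = 20.4, E1 = 60·0.02·13.1 = 15.72, z = 0.78.
- Post-randomisation count: E0 = 15.6, E1 = 10.92, z = 0.90, which is 16% higher. With k = 1 the z values are 0.68 and 0.82, a gain of 20%.

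| Events per week (k = 0) | Power, planned count | Power, post-randomisation count |
|---|---|---|
| 0.01 | 8.5% | 9.8% |
| 0.02 | 12.1% | 14.8% |
| 0.04 | 19.5% | 24.8% |

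**Simulation** (1,500 runs, 0.02 events per week, Poisson GEE with robust standard errors). With true RR 0.70, the median estimate was 0.76 for the planned count and 0.69 for the restricted count. With RR 1.0, rejection rates were 0.049 and 0.047.

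**Recall error.** Suppose a fraction m of weeks 1-4 events is misdated as later, and as many later events as earlier. With x = 4m, the week-13 ratio is (x + (9 − x)·0.70)/9. At m = 0.2 it is 0.727, a loss of about 10% instead of 35%, and z over weeks 5-17 is 0.84, still 9% above the planned 0.78. The gain in z vanishes at about m = 0.43.

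**The case against.** The strongest reply is that little depends on this. The test is valid, the outcome is secondary and unpowered, the week-17 count is clean, and the error is toward no effect. At 0.02 events per week and RR 0.70, the approximate 95% intervals are 0.40 to 1.49 around 0.77 and 0.32 to 1.52 around 0.70, so the shift is small beside either interval. The dilution is also confined to the ratio: the expected absolute difference is 0.078 events per person with either count. All of this is correct. It limits the weight of the point but leaves the planned ratio estimating the wrong window.

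The telephone survey is listed in Appendix I but not supplied, so it may already ask for dates. That stands as a caveat, though the analysis text makes no use of dates. Adverse event reports might place some events in time, but section 10.0 does not make their capture systematic. Call length also differs between groups (40 against 10 minutes), so they are not an even-handed substitute.

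Two further limits stand. The size is assumed and rests on a Poisson ratio of totals; a zero-inflated model would split the group effect, and no attenuation was computed for that case. A delayed effect would dilute the restricted count too: if it began at week 9, RR 0.70 would appear as (4 + 6.3)/13 = 0.79 restricted and (8 + 6.3)/17 = 0.84 planned.

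Finally, participants know whether counselling was added, so misdating around week 4 could differ by group. Suppose there is no true effect and 20% of weeks 1-4 events (0.8 weeks' worth) move later in the SMSH-alone group only. The week-13 ratio would then be 9/9.8 = 0.92 and the weeks 5-17 ratio 13/13.8 = 0.94. The full-window count is immune to this, which is a good reason to keep it alongside.

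**Conclusion.** The concern holds. The recall periods and the timing of the second randomisation put about 4 of the 13 weeks in the week-13 count before the Aim 2 comparison, and the plan neither removes nor adjusts for them. With a uniform rate and true ratios of 0.5 to 0.9, 32% to 39% of the log effect is lost at week 13 and 24% to 30% over both counts. The expected ratio depends on the share of events in weeks 1-4, not on the absolute rate. Type I error is not inflated, and the gain in power is about 1 to 5 percentage points in the cases examined. The Aim 1 service-use analysis and all symptom analyses are unaffected. This should be corrected, chiefly so that the reported ratio describes the period the aim names.

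**What to change.** 1. In the week-13 and week-17 interviews, record the date or study week of each hospitalisation and each ED or urgent care visit. Use the date of the participant's own week-4 call as the landmark. Do this in all arms, so that data collectors stay blinded as section 8.0 intends.
2. For Aim 2, count only events after the second randomisation (about 9 weeks at the week-13 interview and 4 at week 17), with log follow-up weeks as an offset. Use the weeks 1-4 count as a covariate, parallel to week-4 symptom severity.
3. Keep the planned weeks 1-17 count as a sensitivity analysis; it also guards against misdating that differs by group. The absolute difference in mean events can be reported beside the ratio at no extra cost.
4. Leave the Aim 1 service-use analysis and the symptom analyses as written.

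If interviews are already complete without dates, report the week-17 count alone as an unattenuated sensitivity analysis and state the attenuation of the main estimate. The week-17 count is less precise: expected z is 0.357/√(1/4.8 + 1/3.36) = 0.50, against 0.78 for the planned count, at RR 0.70 and 0.02 events per week.

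The cost is one item per reported event in interviews that already take place, in both languages, with a short interviewer briefing and SAP wording. No extra participants or contacts are needed. The downsides are imprecise recall of dates near week 4, the loss of weeks 1-4 events from the Aim 2 count and, if the item is introduced mid-study, dates for later participants only.

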7.0 DETAILED DESCRIPTION OF INTERVENTION

Describe in detail for intervention studies or indicate otherwise by checking below:

Interventions. We deliver interventions via the telephone (see section C2e for rationale) at convenient times for both the survivor and caregiver, including evenings and weekends.

Symptom Management and Survivorship Handbook (SMSH) is an evidence-based self-care management guide specific to each symptom.⁸⁴⁻⁸⁷ Each module is presented in an identical format (frequently asked questions): what the symptom is, how people describe the symptom, the causes of the symptom including medications, and a set of

strategies presented in bullet points for managing the symptom. For each symptom, there are indications as to when and for what reasons to contact the oncology practice; other resources for management are listed. The previously tested English version will be translated into Spanish using an adaptation of Brislin's translation/back translation process²⁴⁰ used by this team in the past. [name], Director of the Undergraduate Translation and Interpretation Program at the University of Arizona, will oversee the translation. Cultural experts will perform back translations of a random sample of pages from the SMSH for comparison to the original English language versions, and all discrepancies corrected between the back translated and original English language pages. Finally, a focus group of six Spanish-speaking Latinos will discuss the translation in terms of understandability (language level and complexity), use of idioms, and consistency of meaning. Focus group data will be used to finalize the SMSH translation and layout (i.e. design).

Survivors and caregivers will be mailed the Handbook in the participant's preferred language following the baseline interviews. During each week, staff will call the survivors and then their caregivers. The call will begin with the assessment of symptoms using the General Symptom Distress Scale (GSDS, described in measures). For each symptom rated at 4 or higher on a 0-10 scale of severity, the survivors will be referred to the SMSH for

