| 8 | Termination of counseling, review successes, reviews social support, stress and coping strategies. Future planning recommendations for follow-up treatment (e.g. antidepressants or continued counseling), framing successes and failures. Discuss options and referrals as needed. Resources available locally and nationally for survivors and their families, including financial, insurance ¹⁷² and legal information ¹⁷³ (session slightly longer). |

Telephone Interpersonal Counseling Intervention (TIP-C). Social work counselors with a master's degree and behavioral health and oncology expertise will deliver the 8-week TIP-C intervention (Table 2).

During weekly contacts, the counselors target social support behaviors using interpersonal communications techniques. Interpersonal communication facilitates processing stressful affective reactions to a cancer diagnosis and treatment, marshalling instrumental support for assistance with roles and functions, informational support for advice and information, and appraisal support for gauging and adjusting to the stressor. Counselors can personalize the counseling intervention for the specific needs or interests as expressed during sessions while still adhering to a structured protocol. For example, one survivor may need to focus on depression and family issues (e.g., role transitions such as job loss) rather than on anxiety and resource issues (e.g., transportation, lack of insurance). This approach is consistent with survivorship care recommendations²⁴¹ and recent evidence showing that improved psychological well-being occurs when an intervention addresses practical resource needs.²⁴²

Each survivor and caregiver receiving the TIP-C+SMSH intervention will receive one 40-minute telephone call per week for 8 weeks (8 sessions). The first 10 minutes of the call will follow the SMSH only intervention procedures (see C8c). The next 30 minutes will be devoted to the delivery of TIP-C. The TIP-C sessions will incorporate the symptoms assessment performed at the beginning of the call as follows: discussion of depression, anxiety and stress per protocol and referral to the SMSH for symptoms. The final 4 weeks will be SMSH only. The TIP-C intervention protocol is the same for both survivor and caregiver, the same counselor will be assigned to both members of the dyad and sessions conducted in either Spanish or English.

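### For the weekly GSDS outcomes, the analysis windows open with a rating taken before the first TIP-C session (week 5 in Aim 2, week 1 in Aim 1), which dilutes the tested group effect

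*Combined protocol and SAP*

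**What the plan says.** **Outcome windows.** Under Analytic Methods in section 5.0, repeated in section 8.0, Hypothesis 1 covers depression, anxiety and "summed severity of other symptoms at weeks 1-12, 13, and 17". For Aim 2 the same strategy "will be implemented for the repeated outcome measures during weeks 5-12 and weeks 13 and 17", adjusted for week-4 severity. Time enters as a class variable and the test is of the group main effect. No group-by-time term, lag or exclusion of the first occasion is stated.

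**Order within a call.** Section 7.0 says of the SMSH call: "The call will begin with the assessment of symptoms using the General Symptom Distress Scale". From week 2 a check of SMSH use comes just before the GSDS. For TIP-C+SMSH calls: "The first 10 minutes of the call will follow the SMSH only intervention procedures (see C8c". The remaining 30 minutes are TIP-C. The section adds that the TIP-C session draws on the symptom assessment already made at the start of that call.

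**Timing of TIP-C.** There is one call a week for eight sessions. After the first randomization the arm is "TIP-C+SMSH for 8 weeks followed by continued SMSH alone for 4 weeks", so the text puts session 1 in week 1. Re-randomized non-responders "have TIP-C added during weeks 5-12", so their session 1 falls in week 5.

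**Sample size.** Section 4.0 enlarges the Aim 2 effect size for the "reduction in error variance due to 10 repeated measures of primary outcomes". Weeks 5-12 plus 13 and 17 make ten, so week 5 is one of them.

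**The concern.** The survivor's week-5 GSDS in Aim 2, and week-1 GSDS in Aim 1, are recorded minutes before that survivor's first TIP-C session. Up to then the survivor's own care has been the same on both sides of the comparison. A rating that cannot reflect the survivor's own counseling is nevertheless averaged into the effect of that counseling. A class variable for time absorbs the time course common to both groups, but it does not let the group difference vary by week.

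At stake are an estimate that understates what TIP-C adds and an avoidable loss of power. Aim 2 matters most, because section 4.0 derives the whole sample size from that comparison.

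**Working it through.** **Inputs.** From section 4.0: adjusted d=0.54, 60 per group for Aim 2, two-sided 0.05, target power .80, 10 repeated measures, correlations between pairs of measures r=0.36 to 0.77, and 172 versus 60 dyads for Aim 1. From sections 5.0 and 8.0: m=10 occasions in Aim 2 and m=14 in Aim 1 (weeks 1-12, 13, 17).

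**Assumptions.** Data are complete, occasions carry equal weight (exchangeable correlation), the effect is zero at the first occasion and constant afterwards, and d=0.54 is taken as given. The last cannot be checked: averaging 10 exchangeable measures turns 0.39 into 0.39/√[(1+9r)/10], which is 0.60 at r=0.36 and 0.44 at r=0.77. Neither end gives the plan's 0.54 to 0.84.

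**Step 1: the plan's own figure.** Noncentral t, noncentrality d√(n/2) = 0.54 × √30 = 2.96, 118 degrees of freedom: power 0.835. The plan's claim of .80 or greater is reproduced.

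**Step 2: Aim 2 with week 5 kept.** Effective d = 0.54 × (m−1)/m = 0.54 × 9/10 = 0.486. Noncentrality 0.486 × √30 = 2.66: power 0.752. By the normal approximation, 67 per group would be needed for .80 at this effect.

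**Step 3: Aim 2 with week 5 dropped.** The full effect applies to 9 occasions, at a slightly larger variance of the mean. The multiplier on d is √{[(1+9r)/10] / [(1+8r)/9]}.

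- r=0.36: √(0.424/0.4311) = 0.992, d=0.536, power 0.829.
- r=0.77: √(0.793/0.7956) = 0.998, d=0.539, power 0.834.

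| Aim 2, 60 per group | d | Power |
|---|---|---|
| Plan, full effect at all 10 occasions | 0.540 | 0.835 |
| Week 5 kept, no effect there | 0.486 | 0.752 |
| Week 5 dropped, 9 occasions | 0.536 to 0.539 | 0.829 to 0.834 |

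**Step 4: Aim 1.** Keeping week 1 gives 13/14 = 0.93 of the estimate obtained without it. This is not 0.93 of the full TIP-C effect, because 60 of the 172 SMSH-alone dyads get TIP-C from week 5. Under the same constant-effect assumption:

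- week 1: contrast 0;
- weeks 2-5 (4 occasions): full contrast;
- weeks 6-13 and 17 (9 occasions): (172−60)/172 = 0.651 of it.

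The average is (4 + 9 × 0.651)/14 = 0.70 with week 1 kept and (4 + 9 × 0.651)/13 = 0.76 with it dropped. The ratio is again 0.93. Most of the dilution in Aim 1 comes from the design itself.

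**The case against.** **The windows match the stated hypotheses, and averaging over the whole period including onset is a legitimate estimand.** This stands in part: the randomized comparison remains valid. A reader might infer a biased test or a raised false-positive rate, but the documents support neither, since the consequence is attenuation. Still, the hypotheses as worded predict a benefit at an occasion before the survivor has had any TIP-C.

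**Not every outcome is affected.** This stands. PROMIS depression and anxiety, also listed under primary outcomes in section 6.0, are taken only at baseline and weeks 13 and 17. Service use and the mediators are not weekly outcomes either.

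**Caregivers are different.** This stands. Section 7.0 has staff call survivors and then caregivers. If that order holds in TIP-C weeks, the caregiver's first rating may follow the survivor's first session, and the plan expects partner effects. To say that TIP-C cannot yet have acted is therefore too strong for caregivers.

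**The power loss is conditional.** This stands. The 0.39 comes from a table not available here, and it may already average over an intervention period. A reader might infer that the trial is shown to be underpowered; the documents do not establish that. Nor do they support a larger loss based on serial correlation. That is possible, but no covariance structure is named and the quoted correlations are for pairs of measures, not adjacent weeks.

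**Dropping an occasion departs from intent to treat.** This does not stand. Every randomized dyad stays in its assigned group; only the occasions that count as outcomes change.

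**Conclusion.** The point holds for the weekly GSDS models. For survivors, the first rating in each window precedes any TIP-C, and the planned main effect averages it in. In Aim 2 this leaves 9/10 of the effect, with power about 0.75 rather than 0.83 at 60 per group. That rests on equal weights, a constant effect after session 1, complete data and an unverified d=0.54. In Aim 1 only the 13/14 ratio can be claimed; reading it as 0.93 of the true TIP-C effect would overlook the SMSH-alone dyads who later receive TIP-C. The order of events is clear from the text; the size is conditional. This is an avoidable loss of sensitivity that should be corrected, and the planned test remains valid.

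**What to change.** 1. First reconcile Table 4 in section 9.0 with the text. The table shows telephone delivery under weeks 2-4 and 2-12 and has no week-1 column, while sections 2.0 and 5.0 describe weekly contacts in weeks 1-12. If delivery began in week 2 and a week-1 rating were still taken, Aim 1 would have two ratings before TIP-C.
2. Before any unblinded analysis, amend the aims in section 2.0 and the hypotheses in sections 5.0 and 8.0 so that the GSDS window opens at the first rating after TIP-C session 1. That is week 6 for Aim 2, and week 2 for Aim 1 if delivery starts in week 1. Alternatively, prespecify a group-by-time model whose primary contrast averages over the occasions after session 1.
3. Keep baseline (Aim 1) and week 4 (Aim 2) as covariates, and report the week-1 and week-5 ratings as a pre-TIP-C check of balance.
4. In section 4.0, change the 10 repeated measures to 9.

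The cost is wording and one figure, with no new data or participants. The downside is one fewer repeated measure per comparison, which costs Aim 2 less than 0.01 in power under the assumptions above. A window chosen after unblinding would look data-driven, so the timing matters.
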